2.2. Secondary

The secondary objectives are as follows:

- To determine the safety profile of MEDI0457 in combination with durvalumab in patients with recurrent/metastatic HPV 16- or 18- associated cancer,
- To evaluate the PFS and OS of patients with recurrent/metastatic incurable HPV-16/18 positive solid malignancies receiving the combination of MEDI0457 and durvalumab,

Version Number: 1.8 Date: July 26, 2019 Proprietary of MD Anderson Cancer Center

• To evaluate ORR by immune-related criteria of the combination of MEDI0457 and durvalumab in patients with recurrent/metastatic incurable HPV-16/18 positive solid malignancies, and

• To evaluate the disease control rate at 24 weeks.

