3.5. Criteria for Withdrawal

A patient will be considered to have completed the study when he/she completes all protocol specified scheduled study visits. The follow-up visit will be the last study visit.

If a patient discontinues or is withdrawn at any time after initiation of study treatment, the investigator should make every effort to have the patient complete all assessments designated for the follow-up visit. The investigator will make every effort to have all scheduled assessment blood samples collected as indicated in **Table 3**. Any AEs present at the time of discontinuation/withdrawal should be followed in accordance with the safety requirements outlined in Section 7.

Patients who discontinue study treatment will be followed for: (1) up to 90 days after last study treatment with durvalumab and/or MEDI0457; (2) until AE/SAE resolution or an outcome is reached for all events (see Section 7.4.2); or (3) until patient initiates alternative anticancer therapy. Patients who leave the study because of a serious or significant safety issues should be followed closely until the AEs are fully and permanently resolved or stabilized (if complete resolution is not anticipated), with the follow-up data recorded in the database (see Section 7.4.2 for further details regarding the follow-up of unresolved AEs).

If a patient discontinues from treatment for reasons other than disease progression, and therefore continues to have tumor assessments, drug or procedure-related SAEs must be captured until the patient is considered to have confirmed PD and will have no further tumor assessments.

Investigator should discuss the reason for any discontinuation of study treatment with the MDACC IND Office Medical Monitor prior to any action or within 24 hours when information becomes available.

The primary reason for the patient discontinuing study treatments or withdrawal from the study should be among the following standard categories.

• Adverse Event: Clinical or laboratory events occurred that, in the medical judgment of the investigator for the best interest of the patient, are grounds for discontinuation. This includes serious and non-serious AEs regardless of relation to study treatment.

Version Number: 1.8
Date: July 26, 2019

Proprietary of MD Anderson Cancer Center

• Death.

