5. STUDY PLAN

All study procedures will be performed according to **Table 3**.

Version Number: 1.8 Date: July 26, 2019

Proprietary of MD Anderson Cancer Center

Table 3. Schedule of Study Procedures

	Screening	(Cycle 1		Cyc	ele 2	Cy	cle 3	Cycle 4 ^a	Cycle 5 ^a	EOT ^b	Follow-up ^c
Week of Study	-	1	3	4	7	8	10	12	16	20	-	-
Procedures Day of Week	-28 to -1	1 ±7 days (unless otherwise noted)										
Informed consent	X											
Demographics	X											
Medical histories ^d	X											
Inclusion/exclusion criteria	X	X										
Physical examination ^e	X	Xf	X	X	X	X	X	X	X	X	X	
ECOG performance status	X	X^{f}	X	X	X	X	X	X	X	X	X	
Adverse events assessment	X	X	X	X	X	X	X	X	X	X	X	
Concomitant medications/procedures	X	X	X	X	X	X	X	X	X	X	X	
Disease status ^g	X ^h							Xi		X ^{i,j}	X	X^k
Hepatitis/HIV screening ¹	X											
Vital signs ^m	Xg	Xf	X	X	X	X	X	X	X	X	X	
12-lead ECG	X	Xf				X		X		X ⁿ	X	
HPV typing ^o	X											
Hematology ^p	X	Xf	X	X	X	X	X	X	X	X^q	X	
Serum chemistry ^r	X	Xf	X	X	X	X	X	X	X	X^q	X	
Coagulation testing ^s	X	As clinically indicated.										
Thyroid function testing ^t	X	X^{f}		X		X		X	X	X^q	X	
Urinalysis ^u	X	As clinically indicated.										
Pregnancy test ^v	X^{w}	X ^x		X		X		X	X	X	X	
MEDI0457 administration ^y		X	X		X			X		X		
MEDI0457 post-treatment reaction ^z		X	X		X			X		X		
Download EP data		X	X		X			X		X		
Durvalumab administration ^{aa}				X		X		X	X	X		
Tumor biopsy ^{bb}	X						Xcc				X^{dd}	
Immune Profiling/HPV Serology Research Bloodee		X		X		X	X		$X^{\rm ff}$		X	
Pharmacokinetics/ADA Research Blood ^{gg}				X		X			X^{hh}			
Viral load ⁱⁱ	X			X		X		X	X	X	X	
HBV DNA/Hep BsAg ^{jj}				X		X		X			X	

Version Number: 1.8

Proprietary of MD Anderson Cancer Center Date: July 26, 2019

- ^a Patients can continue on the study until progression or unacceptable toxicity as long as the physician feels the patient is receiving benefit. Cycles 4 and 5 should be repeated to continue this treatment. ^b End of treatment (EOT) is defined as the last visit where the decision is made to discontinue protocol directed treatment.
- ^c A clinic visit is not required for follow-up. Patients who are taken off study due to disease progression or intolerable toxicities will be followed for vital status every 6 months via phone and/or review of medical record.
- ^d Histories include medical history, history of prior cancer treatment, history of procedures

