Patients who discontinued from treatment for reasons other than PD will continue disease assessments until confirmed PD or start of subsequent anticancer therapy.

The response to immunotherapy may differ from the typical responses observed with cytotoxic chemotherapy including the following:

- Response to immunotherapy may be delayed,
- Response to immunotherapy may occur after PD by conventional criteria,
- The appearance of new lesions may not represent PD with immunotherapy, and/or
- SD while on immunotherapy may be durable and represent clinical benefit.

Based on the above-described unique response to immunotherapy and based on guidelines from regulatory agencies, e.g., European Medicines Agency's "Guideline on the evaluation of anticancer medicinal products in man" (EMA/CHMP/205/95/Rev.4) for immune modulating anticancer compounds, this study will include the following in addition to standard RECIST 1.1 criteria:

- RECIST will be modified so that PD must be confirmed with a second radiologic assessment, preferably, 5 weeks (+/- 7 days) after the initial assessment of PD in the absence of clinically significant deterioration. Treatment with study regimen should continue between the initial assessment of progression and confirmation for progression at outlined in Tables 4.
- In addition, subjects may continue to receive the study regimen beyond confirmed PD in the absence of clinically significant deterioration and if investigators consider that subjects may be deriving benefit from treatment and there are no more suitable alternative treatments available for the subject.

Version Number: 1.8

Proprietary of MD Anderson Cancer Center Date: July 26, 2019

Modification of RECIST as described is meant to discourage the early discontinuation of the study regimen and provide a more complete evaluation of its anti-tumor activity than would be seen with conventional response criteria. Nonetheless, the efficacy analysis will be conducted by programmatically deriving each efficacy endpoint based on the first evidence of progression (by modified RECIST 1.1 criteria described below) when progression is confirmed by a second scan.

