RECIST version 1.1 assessment/scans contributing towards a particular visit may be performed on different dates. The following rule will be applied:

For investigator assessments, the date of progression will be determined based on the earliest of the RECIST version 1.1 assessment/scan dates of the component that indicates progression.

When censoring a patient for PFS, the patient will be censored at the latest of the dates contributing to a particular overall visit assessment.

Note: For target lesions, only the latest scan date is recorded out of all scans performed at that assessment for the target lesions, and similarly for non-target lesions, only the latest scan date is recorded out of all scans performed at that assessment for the non-target lesions.

PFS will be assessed in the Response-evaluable and As-treated populations.

8.3.2.3. **Disease Control Rate (DCR)**

Disease control rate is defined as N (%) patients with CR, PR, or SD by 24 weeks on study using RECIST version 1.1. For SD determination for DCR, the patient must have lack of progression for the first 24 weeks on study. Disease control rate will be assessed in the Response-evaluable and As-treated populations.

8.3.2.4. **Overall Survival (OS)**

OS is defined as the time from the date of start of IP treatment until death (+1 day) due to any cause. Any patient not known to have died at the time of analysis will be censored based on the

Version Number: 1.8 Date: July 26, 2019

Proprietary of MD Anderson Cancer Center

last recorded date on which the patient was known to be alive. OS will be assessed in the Response-evaluable and As-treated populations.

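### Survival follow-up depends on why a patient stopped: Section 3.5 and Table 3 note c are not reconciled, and some patients have no required vital-status check once new therapy starts

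*Combined protocol and SAP*

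**What the plan says.** Section 2.2 lists among the secondary objectives: "To evaluate the PFS and OS of patients with recurrent/metastatic incurable HPV-16/18 positive solid malignancies". Section 1.3.2 names OS among the secondary endpoints that will inform the decision on further studies. Section 8.3.2.4 defines the endpoint: "OS is defined as the time from the date of start of IP treatment until death (+1 day) due to any cause". A patient not known to have died is censored at the "last recorded date on which the patient was known to be alive".

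Three places govern what is collected after treatment stops:

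- **Section 3.5:** "Patients who discontinue study treatment will be followed for: (1) up to 90 days after last study treatment with durvalumab and/or MEDI0457"; or until AE/SAE resolution or outcome; or, as the last item, "3) until patient initiates alternative anticancer therapy". No rule says whether the earliest or the latest item applies. Survival is not mentioned.
- **Table 3, note c (Section 5):** "Patients who are taken off study due to disease progression or intolerable toxicities will be followed for vital status every 6 months via phone" or by record review. No end date is given, and new therapy does not stop it.
- **Section 6.3 and Table 3, note g:** patients who stop for reasons other than progression "will continue disease assessments until confirmed PD or start of subsequent anticancer therapy". Note k sets the scan schedule for patients without progression: Day 90, then every 3 months to Month 12, then every 6 months to end of study.

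No section gives an OS data cut-off or a length of survival follow-up.

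**The concern.** OS counts death from any cause at any time, so it needs vital status on every treated patient, whatever the reason for stopping. Here the requirement depends on that reason. If stopping or switching is related to prognosis, the last date known alive is an informative censoring time, and the Kaplan-Meier curve no longer estimates survival of the treated population.

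Section 3.5 adds a second problem. A site could read it as the general follow-up rule and stop contact at 90 days or at new therapy. The number of deaths recorded would then depend on which passage the site follows. The trial has a single arm, so no comparator shares the error.

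**Working it through.** **1. Which patients are uncovered.** Take the reasons for stopping in Sections 3.4 and 3.5 and ask which passage requires a survival date after new therapy starts.

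| Reason for stopping | Vital status (note c) | Scans (6.3, notes g and k) | Required after new therapy |
|---|---|---|---|
| Progression | Every 6 months | No longer needed | Vital status continues |
| Intolerable toxicity | Every 6 months | Until confirmed PD or new therapy | Vital status continues |
| Physician decision, non-compliance, refusal of further drug, switch before confirmed PD | Not required | Until confirmed PD or new therapy | Nothing |
| Withdrawal of consent to all follow-up | Not permitted | Not permitted | Nothing |

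The third row is the gap. It may include patients whose disease is failing: Section 6.3 describes rapid progression that needs other anticancer therapy, which could come before a confirming scan. Note c does not say whether unconfirmed progression counts.

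The second item in Section 3.5 (AE/SAE outcome) does not close the gap. Section 7.4.2 follows unresolved events without further entry in the case report form and, after 90 days, only for ongoing drug-related SAEs.

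**2. Size of the effect.** The plan states no OS median, landmark, event count or power, so there is no figure to reproduce. The documents give no rates either. Every rate below is an assumption, in monthly hazards:

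- progression 0.15 or 0.25
- stopping for another reason 0.02 or 0.05
- stopping for toxicity 0.02
- death before progression 0.01; after progression 0.09
- new therapy 0.5 after progression, 0.2 otherwise
- death after a switch without progression: 0.5, 1 or 2 times the post-progression hazard
- data cut-off 30 months

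This gives 2 x 2 x 3 = 12 scenarios, each with 200,000 simulated patients. Survival is the product over death times of (1 - deaths / number at risk). Bias is the 12-month estimate under a given follow-up rule minus the 12-month value with full follow-up. The simulation error of one estimate is about sqrt(0.5 x 0.5 / 200,000) = 0.001.

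Follow-up rules compared:

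- A: Section 3.5 alone, everyone censored 90 days after stopping.
- B: Section 3.5 alone, everyone censored at the earlier of 90 days or new therapy.
- C: note c with Section 6.3, so only other-reason stoppers who switch before progression are lost, at the switch.
- D: note c in force, but all other-reason stoppers lost 90 days after stopping.

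| Scenario (progression; other stop; multiplier) | Full follow-up | A | B | C | D |
|---|---|---|---|---|---|
| 0.15; 0.05; 2 | 0.516 | 0.643 (+0.127) | 0.739 (+0.223) | 0.550 (+0.034) | 0.540 (+0.024) |
| 0.15; 0.05; 1 | 0.538 | 0.655 (+0.117) | 0.738 (+0.200) | 0.548 (+0.010) | 0.545 (+0.007) |
| 0.25; 0.05; 0.5 | 0.480 | 0.573 (+0.093) | 0.662 (+0.182) | 0.472 (-0.008) | 0.473 (-0.007) |
| Bias, all 12 scenarios | 0.455 to 0.558 | +0.093 to +0.127 | +0.182 to +0.223 | -0.008 to +0.034 | -0.007 to +0.024 |

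Median OS with full follow-up is 10.9 to 13.6 months. Rule A adds 3.4 to 6.2 months. Rule C moves the median by about -0.3 to +0.9 months.

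**3. What drives the sign under rule C.** The patients lost are 3% to 12% of the total. In the four scenarios where they die at half the post-progression hazard, OS is understated; in the eight where they die at that hazard or twice it, OS is overstated. For scale, the sampling standard error of a 12-month OS near 0.5 in 77 patients, ignoring censoring, is sqrt(0.5 x 0.5 / 77) = 0.057.

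**The case against.** The best defence is that Section 3.5 is a safety rule and Table 3 is the follow-up rule. The 90-day sentence stands among sentences on adverse events and cites Section 7.4.2. The same 90 days is the AE/SAE window in Sections 7.2 and 7.4.1. Section 5 says that all procedures follow Table 3. Note c tracks patients who stop for progression or toxicity, with no stop at new therapy, and note k keeps patients without progression under assessment long past Day 90. Section 8.3.2.4 does not censor at 90 days or at new therapy. OS is secondary and descriptive, with no hypothesis or event target.

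Most of this stands. A reader might infer that survival follow-up ends for everyone at 90 days or at new therapy, and that OS is therefore overstated. The documents do not support that. The large figures under rules A and B require a site to disregard note c, and they come mainly from censoring patients with progression, whom note c tracks. Nor can one assume that all untracked patients do worse: pregnancy, ineligibility and non-compliance are also reasons for stopping in Section 3.4.

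Two things remain. Section 3.5 does not say that it is limited to safety, and its new-therapy item fits a safety rule poorly, because the AE/SAE windows in Sections 7.2 and 7.4.1 have no such stop. And even on the most favourable reading, the other-reason group has no required vital-status check after new therapy. Censoring at the last date known alive is only as good as the dates collected.

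**Conclusion.** The point holds as a gap in follow-up and an unreconciled pair of passages, not as a demonstrated overstatement of survival. With note c in force, OS may be informatively censored, but the bias is probably small, about -1 to +3 percentage points at 12 months, and its direction is undetermined. If a site lets Section 3.5 override note c, the overstatement is clear, about +9 to +22 points. All these figures rest on assumed hazards and are illustrations, not estimates for this trial. The primary ORR analysis is not affected. The correction is worth making because the plan itself writes the selective follow-up, OS feeds the decision on further studies, and the remedy is cheap.

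**What to change.** 1. In Section 3.5, state that the three limits apply to safety follow-up only, and refer to Table 3 for survival.
2. In Table 3 note c, remove the restriction by reason for stopping. Follow every patient who received any study drug for vital status, by phone or record review, whether or not new therapy has started, until death, withdrawal of consent to follow-up, or a stated OS data cut-off.
3. Separate refusal of further drug from withdrawal of consent to follow-up, so that only the latter ends vital-status collection.
4. Give the OS data cut-off in Section 8.3.2.4, and do one vital-status sweep of all treated patients just before the OS analysis.

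The cost is a few wording changes and some extra phone or record checks. The six-monthly process already exists. Under the assumed rates the patients now missed are 3% to 12% of 77, that is 0.03 x 77 = 2 to 0.12 x 77 = 9, plus any among treated patients who are not evaluable. Patients who withdraw consent to all follow-up remain censored, as Section 3.5 requires.

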3.5.1. Screen failures

Screen failures are patients who do not fulfill the eligibility criteria for the study, and therefore must not be enrolled into the study. These patients should have the reason the patient does not meet the required inclusion/exclusion criteria for study withdrawal recorded. This reason for study withdrawal is only valid for screen failures.

3.5.2. Withdrawal of the informed consent

Patients are free to withdraw from the study at any time (IP and assessments) without prejudice to further treatment.

A patient who withdraws consent should always be asked about the reason(s) and the presence of any AE. The investigator should follow-up AEs outside of the clinical study. If possible, they will be seen and assessed by an investigator(s), and AEs will continue to be followed (see Section 7).

If a patient withdraws from participation in the study, then his/her enrollment number cannot be reused.

4. INVESTIGATIONAL PRODUCTS

4.1. Identity of Investigational Products

4.1.1. MEDI0457

MEDI0457 is a plasmid DNA vaccine consisting of three plasmids as a 3:3:1 (w/w) combination of pGX3001, pGX3002 and pGX6001.

Version Number: 1.8 Date: July 26, 2019

Proprietary of MD Anderson Cancer Center

MEDI0457 will be supplied in a single pre-filled 2 mL glass vial containing all three components. The minimum fill volume for MEDI0457 vials is 1 mL.

Vials must be stored at -25°C to -15°C (-13°F to 5°F) inside a -20°C freezer at all times upon receipt at the clinical site. A freezer temperature log must be monitored daily and maintained at the site.

4.1.1.1. pGX3001

Chemical name: Circular double-stranded DNA plasmid consisting of 3782 base pairs.

Distinguishing name: Eukaryotic expression plasmid containing HPV-16 E6 and E7-encoding transcription unit controlled by a synthetic, cytomegalovirus promoter, and elements required for replication and selection in *E. coli*, namely a pUC origin of replication (pUC Ori) and a kanamycin resistance gene (Kan R).

4.1.1.2. pGX3002

Chemical name: Circular double-stranded plasmid DNA consisting of 3824 base pairs.

Distinguishing name: Eukaryotic expression plasmid containing HPV-18 E6 and E7-encoding transcription unit controlled by a synthetic, cytomegalovirus promoter, and elements required for replication and selection in E. coli, namely a pUC origin of replication (pUC Ori) and a kanamycin resistance gene (Kan R).

4.1.1.3. pGX6001

Chemical name: Circular double-stranded plasmid DNA consisting of 6259 base pairs.

Distinguishing name: Eukaryotic expression plasmid containing synthetic interleukin-12 p35 light chain and p40 heavy chain (pGX6001) controlled by a dual promoter vector, a bGH poly A tract, bacterial origin of replication to support production of the plasmid in *E. coli*, and a kanamycin resistance gene (Kan R).

4.1.2. Durvalumab

Durvalumab (also known as MEDI4736) is a human IgG1 kappa monoclonal antibody directed against human PD-L1. Durvalumab selectively binds human PD-L1 with high affinity and blocks its ability to bind to PD-1 and CD80. The fragment crystallizable domain of durvalumab contains a triple mutation in the constant domain of the IgG1 heavy chain that reduces binding to the complement component C1q and the Fc γ receptors responsible for mediating antibody dependent cell mediated cytotoxicity (Oganesyan et al 2008).

Durvalumab will be supplied by AstraZeneca/MedImmune or its designee as a 500 mg vial solution for infusion after dilution. The solution contains 50 mg/mL durvalumab, 26 mM histidine-hydrochloride, 275 mM trehalose dihydrate, and 0.02% (w/v) polysorbate 80; it has a pH of 6.0. The nominal fill volume is 10.0 mL. IP vials are stored at 2°C to 8°C (36°F to 46°F) and must not be frozen. Durvalumab must be used within the individually assigned expiry date on the label.

Version Number: 1.8 Poter July 26, 2019 Proprietary of MD Anderson Cancer Center

4.1.3. **CELLECTRA®5P** device for in vivo electroporation

The use of EP via the CELLECTRA®5P device increases the immunogenicity of MEDI0457. Electroporation utilizes a transmembrane electric field pulse to induce microscopic pathways (pores) in a bio membrane. The electric field allows macromolecules, ions, and water to pass from one side of the membrane to the other. The presence of a constant field influences the kinetics of directional translocation of the macromolecular plasmid, such that the plasmid delivery in vivo has been sufficient to achieve physiological levels of secreted proteins. Intramuscular injection of plasmid followed by EP has been used very successfully to deliver therapeutic genes that encode for a variety of hormones, cytokines or enzymes in a variety of species (Prud'homme et al 2006, Prud'homme et al 2007). The design of software that enables constant current EP to deliver plasmids allows for the individual resistance of the treated muscle to be taken into consideration and yields highly efficient in vivo plasmid expression (Khan et al 2005).

The target organ for EP is skeletal muscle. The skeletal musculature is an excellent candidate for the target tissue of gene expression, because muscle fibers have a long lifespan and can be transduced by circular plasmids, allowing the gene to be expressed efficiently in immunocompetent hosts (Davis et al 1993, Tripathy et al 1996). Furthermore, muscle is well vascularized, allowing the newly produced transgene product to gain access to the circulation.

The CELLECTRA®5P) device and its components bear labels that identify the device name and place of business of the manufacturer. The CELLECTRA®5P User Manual describes all relevant contraindications, hazards, adverse effects, interfering substances or devices, warnings, and precautions. Each CELLECTRA®5P Pulse Generator has a unique serial number and each CELLECTRA®5P Applicator has a unique serial number. Each CELLECTRA®5P Array has a Lot Number, Manufacture Date and Expiration Date.

The CELLECTRA®5P device, and its components, will be shipped directly from the manufacturer to 1) the study site or 2) the study depot prior to shipping to the study site. The investigational labels in Section 4.2 below are presented as examples. Please note, information such as expiration date, lot and serial numbers (as applicable) is included at the time of manufacture and may vary from these examples. The information found on the actual device labels should always be used to manage, track and record IP accountability during study conduct.

